5.3 SCREEN FAILURES

Screen failures are defined as participants who consent to participate in the clinical trial but are not subsequently randomly assigned to the study intervention or entered in the study. A minimal set of screen failure information is required to ensure transparent reporting of screen failure participants, to meet the Consolidated Standards of Reporting Trials (CONSORT) publishing requirements and to respond to queries from regulatory authorities. Minimal information includes demography, screen failure details, eligibility criteria, and any serious adverse event (SAE). Subjects who are screened but fail to be enrolled in the study for any reason will be documented on the screening log along with the reason for screen failure.

Individuals who do not meet the criteria for participation in this trial (screen failure) because of because of severe hypoxemia (Exclusion Criterion 11), low hemoglobin (Exclusion Criterion 12), use of high frequency oscillatory ventilation (Exclusion Criterion 21), or use of inhaled pulmonary vasodilators (Exclusion Criterion 23) may be rescreened. Rescreened participants should be assigned the same participant number as for the initial screening.

5.4 STRATEGIES FOR RECRUITMENT AND RETENTION

Thirty-six inpatient subjects will be recruited for this study at four enrolling medical centers. Subjects will be identified by prospective medical record review. We anticipate that the distribution of gender, race, and ethnicity of the subjects enrolled will be similar to the demographic characteristics of ICU patients admitted to each of our participating centers and be proportional to the enrollment distribution. No gender, race, and/or ethnicity group will be excluded from participation in our proposed study.

Study coordinators at each site will screen inpatient ICUs daily to identify all potential subjects based on the pre-defined inclusion and exclusion criteria. The recruitment process will consist of electronic medical record (EMR) review of all intubated patients in the ICUs at each site to determine if a potential subject

meets study eligibility criteria. EMR alerts may also be used to assist research coordinators in the early identification of potential participants that meet study eligibility criteria. The research coordinators at each site will identify potential participants and review the study eligibility criteria in detail with the site PI or designee. No recruitment or advertisement materials will be utilized to recruit patients, however flyers may be posted in ICU staff areas to educate colleagues and other health care providers about study eligibility criteria and the importance of participation in clinical research. We will also engage the ICU clinical communities through conferences and other educational resources at each site as our ICU colleagues will play a critical role in the recruitment, retention, and overall conduct of the clinical trial. Participants will be hospitalized in the ICU at the time of informed consent and throughout the treatment period of the study protocol, thus we do not foresee difficulties in adherence with the study drug treatment. For participants who are extubated prior to completion of the 3-day treatment portion of the protocol, all data will be analyzed on a modified intention-to-treat (MITT) basis. For long-term follow-up outcomes, we will use web-based investigator tools for messaging and scheduling reminders to contact participants.

Several engagement strategies will be adopted to ensure retention of study participants for assessment of long-term outcomes following hospitalization. First, we have designed the study protocol to minimize participant burden in order to optimize subject retention in the trial. We have designed the protocol such that the long-term follow up requires no travel or costs and entails four brief (2-10 minutes) telephone calls at day 28, day 60, 3 months, and 6 months. Second, we have established an efficient tracking system for long-term follow-up. At the time of consent, participants and/or their legally authorized representative (LAR) will be asked to provide email addresses and several phone numbers (home, work, cell) and to indicate the best times to contact them and whether voice and/or text messages can be left.

As many ICU patients are discharged to long-term care facilities following hospitalization, we will consent study participants for permission to contact them at a long-term care facility if applicable. The names and contact information of up to three people who can be contacted for assistance with locating participants will also be requested. Written informed consent to contact these individuals will be obtained, including a description of the scope of the information to be obtained (eg. forwarding addresses versus questions about the clinical status of the participant). In the event of being unable to contact study subjects, we will send letters and/or emails to participants who are unresponsive to personal contact. We will also obtain consent to use social security numbers to determine vital status of participants lost to follow-up.

To mitigate retention risks at the time of consent, we will educate subjects (and their LARs) about their important role as research participants, the requirements of the study, and clearly orient participants to the study demands, tasks, and responsibilities. Most of the patients approached for participation in this research protocol will have limitations of decision-making abilities due to their critical illness or need for sedating medications. Hence, most patients will not be able to provide informed consent and accordingly, informed consent will be sought from the potential subject's LAR. See **Section 10.1.1** for additional information.

We have expanded inclusion criteria to include subjects with unilateral or bilateral infiltrates intubated for suspected lung infection (pneumonia), given similar outcomes from unilateral or bilateral lung infiltrates in critically ill patients, consistency with our preclinical baboon model of ALI due to pneumococcal pneumonia that had improved outcomes with inhaled CO, and the need to expand enrollment for this study.

6 STUDY INTERVENTION

6.1 STUDY INTERVENTION(S) ADMINISTRATION

6.1.1 STUDY INTERVENTION DESCRIPTION

Inhaled CO or placebo air will be administered to mechanically ventilated subjects using a mechanical ventilator approved for inhaled NO delivery and the CO Delivery System developed by 12th Man Technologies (**Figure 3, Appendix A**). See **Appendix A** for details of the CO Delivery Device testing, assembly, calibration, and standard operating procedures (SOP). The CO Delivery System will be calibrated and connected to the ventilator (**Figure 9**) as described in **Appendix A**. As per the SOP and illustrated in the schema in **Figure 9**, the injector module will be connected between the inspiration port of the ventilator and inlet port of the humidifier. The gas sampling line will be placed between the outlet port of the humidifier and the patient wye as shown.

[figure not shown]

Figure 9. Schema of CO Delivery System and ventilator.

The study drug will be administered by an RT and a physician study staff member OR a physician study staff member alone. A physician study staff member will be present at the bedside during and immediately available for an additional 90 minutes after administration of the study drug to address any clinical concerns that arise, or provide any necessary emergency care in conjunction with the subject's clinical ICU team. The administering RT and physician study staff member OR the physician study staff member alone will be unblinded to the treatment assignments and will conceal the gas cylinders and COventDS to assure that the study coordinator and treating ICU team remain blinded to the study drug assignment.

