2.2.7 DELIVERY OF INHALED CO TO MECHANICALLY VENTILATED SUBJECTS

Figure 3. CO Delivery System (12th Man

In order to study inhaled CO in mechanically ventilated subjects with pneumonia and sepsis-induced ARDS, a Carbon Monoxide Delivery System (COeventDS) (**Figure 3**) developed by 12th Man Technologies will be used (**Appendix A- CO Delivery System**). The CO Delivery System is a microprocessor-based constant gas concentration delivery system that can be used to deliver operator-specified concentrations of CO to mechanically ventilated patients. The CO Delivery System delivers an operator set, constant concentration of CO gas into the inspiratory path of the patient breathing circuit independent of the patient's inspiratory flow, while the patient's respiration is supported by a ventilator. For safety reasons, the CO Delivery System has twin microprocessors

such that the division of control is split between a closed loop proportional-integral-derivative (PID) controlled mixing module that is only involved with monitoring the patient flow and mixing of the gases, and an interface module that is the working face to the user for control and monitoring functions. This second microprocessor watches the delivery subsystem, monitors the inspired gas for deviations from the set concentration, and monitors inspired oxygen.

The heart of the system is comprised of three components including an inspiratory flow monitor with a ratio-metric matching CO injector module, an inhaled gas monitoring module, and a gas mixing subject interface/breathing valve for spontaneously breathing subjects. It is a variable inspiratory flow delivery system that matches the patient's inspiratory flow with the injected 5000 ppm CO to deliver the operator set CO concentration on the LCD user interface. It is a breathing-initiated delivery system and the CO is blended into the inspiratory gas stream only as long as flow is being delivered to the patient and at the exact proportions to maintain the desired concentration, independent of any change in breathing pattern, flow rate, respiratory rate, or tidal volume. The analyzer, with alarm functions, monitors the inhaled CO and O₂ concentrations.

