Patients less than 18 years of age are excluded because the participating ICUs do not typically admit pediatric patients and we believe the benefit/risk ratio for children to receive iCO is not appropriate at this early stage. Patients with ARDS or pneumonia with mechanical ventilation for more than 168 hours are excluded in order to evaluate more clearly the effects of iCO early in the course of lung injury. Patients with severe hypoxemia or need for ECMO are excluded because they may not have adequate reserve to tolerate the reduction in oxygen carrying capacity. The parameters of $\text{SpO}_2 < 95$ or $\text{PaO}_2 < 90$ on $\text{FiO}_2 \geq 0.9$ are used rather than a simpler $\text{PaO}_2/\text{FiO}_2$ ratio of 100 to define severe hypoxemia for both enrollment and daily treatment to better account for factors affecting arterial oxygen content and to ensure an additional safety margin during treatment of enrolled subjects. These criteria exclude patients with $\text{PaO}_2/\text{FiO}_2 \leq 100$ ($\text{PaO}_2 90/\text{FiO}_2 0.9$), but also explicitly specify a safety margin of 0.1 for FiO_2 . These criteria are currently approved by the Institutional Review Boards (IRBs) at our participating clinical centers, our DSMB, and the FDA for our Phase II CO ARDS trial (NCT03799874).

Patients with hemoglobin < 7.0 g/dL, Jehovah's witnesses, or patients otherwise unable or unwilling to receive blood transfusions during hospitalization are excluded because of the volume of blood drawn for monitoring during iCO therapy may place these patients at greater risks from complications of anemia. Moribund patients and patients with extensive body surface area burns have a high incidence of AEs and lactic acidosis that will confound the safety assessment. Pregnancy, recent stroke, or cardiac arrest are exclusions because iCO may reduce oxygen delivery to the fetus and recently injured brain respectively. Patients with alveolar hemorrhage from vasculitis are excluded because the mechanism of lung injury is

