6.1.2 CO OR PLACEBO CYLINDERS

The gas cylinders for this clinical trial are AG or A3 aluminum cylinders with a CGA 500 valve and will be supplied by Praxair Healthcare Services (Morrisville, PA). The cylinder contains approximately 360 liters of 5000 ppm (0.5%) CO in room air (21% oxygen) and poses no increased flammability risk. Placebo tanks will contain medical grade air in identical appearing cylinders. The gas cylinder's nominal size is 5 inches in diameter by 17 inches tall. Given the flow limitation from the regulator of ~7 liters per minute and a minimum of 6 air exchanges per hour in an average 15x15x10 ICU room, we do not expect ambient CO levels to exceed the OSHA permissible exposure limit (PEL) of 50 ppm as an 8 hour time-weighted average. We measured ambient CO levels during our animal studies using the COventDS and were unable to detect increases in ambient CO levels throughout assembly, calibration, and delivery of CO to the animals. In addition, we simulated CO administration with an ICU ventilator (Puritan-Bennett 840), CO Delivery System, and lung model in an ICU room at Massachusetts General Hospital at 500 ppm for over 2 hours and ambient CO levels were near zero and well below the OSHA PEL.

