6.2.2 FORMULATION, APPEARANCE, PACKAGING, AND LABELING

The study drug will be provided for this study by Praxair Healthcare Services. Gas mixtures will be manufactured with United States Pharmacopeia (USP)/Ultra High Purity (UHP)/National Formulary (NF) components. The mixtures will be prepared as a Certified Standard with a blend tolerance of $\pm 10\%$ and analytical uncertainty of 2%.

The gas mixture provided to subjects randomized to CO will be 5000 ppm CO (balance air) and will be provided to study sites by Praxair Healthcare Services in AG or A3 aluminum cylinders with a CGA 500 valve. The gas cylinder's nominal size is 5 inches in diameter by 17 inches tall, contains 360 liters of 5000 ppm (0.5%) CO in room air (21% oxygen), and poses no increased flammability risk. The 5000 ppm CO source gas will be administered via the CO Delivery System (12th Man Technologies, Garden Grove, CA) and delivered to subjects at a CFK equation-determined individualized dose (200-500 ppm) to achieve a target COHb level of 6-8%.

The mixture components include: **Carbon Monoxide UHP Grade 3.0** (Assay 99.9%; O₂ < 10 ppm, H₂O < 5 ppm, N₂ < 900 ppm and CO₂ < 20 ppm); and **Medical Air USP**. The source materials for **Medical Air USP** include: **Oxygen USP** (Assay $\geq 99.2\%$; Odor- none; Oxygen produced by air liquefaction process, does not require CO and CO₂ analysis); and **Nitrogen NF USP** (Assay $\geq 99.2\%$; Identification- OK, Paramagnetic Assay Method; CO ≤ 10 ppm; Odor- none).

The gas mixture provided to subjects randomized to placebo will be medical grade air and will be provided to study sites by Praxair Healthcare Services in AG or A3 aluminum cylinders with a CGA 346 valve. With the exception of the 346 valve, the placebo gas cylinders will be identical in size and color as the CO cylinders. The placebo gas will be administered via the CO Delivery System (12th Man Technologies,

Garden Grove, CA) and delivered to subjects in an identical fashion as iCO delivery.

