Concomitant Medications Review: The following medications will be recorded in the study eCRFs: aspirin, COX-2 inhibitors, NSAIDs, ACE inhibitors, steroids, phosphodiesterase inhibitors, neuromuscular blockade, inhaled NO or prostaglandins, antibiotics, diuretics. TPN use will also be recorded.

EKG: A 12 lead EKG will be obtained and reviewed daily by the study staff physician prior to study drug administration to evaluate for cardiac exclusion criteria (acute MI, ACS, or unstable atrial or ventricular arrhythmia). The study drug will not be started until the EKG is obtained and reviewed by the study physician investigator for a potential study hold. The EKG will also be officially read locally at each site.

Fluid Intake/Output: Fluid intake and output (most recent 24 hour value) or mean hourly value for most recently available period. Diuretic administration will also be recorded if applicable.

Glasgow Coma Scale (GCS): The GCS is a determination of the best eye opening, motor, and verbal responses at any given time. The GCS is documented by the clinical team as part of routine ICU nursing assessment. If not available, the GCS will be assessed by the study staff as described in **Appendix B2**.

Lung Injury Score (LIS): The lung injury score will be calculated based on the chest x-ray assessment, PaO₂, FiO₂, PEEP, and ventilator compliance measurement as described in **Appendix B3**.

Microbiological Results: Microbiological results will be recorded in the eCRF when ordered for clinical purposes.

- a) Blood cultures
- b) Urine cultures
- c) Sputum cultures
- d) BAL cultures
- e) CSF cultures if available
- f) Stool
- g) Other

Neurocognitive Testing: Neurocognitive testing will be performed via telephone interviews using the Montreal Cognitive Assessment (MoCA)-BLIND and Hayling sentence completion test as (**Appendix C**).

Oxygenation Index (OI): The OI will be calculated based on the PaO₂, FiO₂, and mean airway pressure obtained from the ventilator parameters.

Renal replacement therapy status: Renal replacement therapy status within the last 24 hours will be recorded.

Richmond Agitation Scale (RASS): RASS is a scale used to measure the agitation or sedation level of a patient. RASS scoring is documented by the clinical team as part of routine ICU nursing assessment. If not available, the RASS will be assessed by the study staff as described in **Appendix B4**.

ScvO2: ScvO₂ will be recorded if available.

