Sequential Organ Failure Assessment (SOFA): The SOFA score will be calculated based on the worst values recorded in the past 24 hours. Calculation variables are described in **Appendix B5**.

- a) Worst PaO₂/FiO₂ for that date
- b) Worst creatinine (or urine output), bilirubin, and platelet count for that date
- c) Worst Glasgow Coma Scale for that date
- d) Vasopressor use and maximal dose for that date

Vasopressors and Inotropes Review: The following vasopressors/inotropes will be recorded in the study eCRFs (epinephrine, norepinephrine, phenylephrine, vasopressin, dopamine, dobutamine, phosphodiesterase inhibitors, including dose).

Ventilator Parameters: The study staff will record ventilator parameters prior to starting study drug administration. The following settings will be recorded:

- a) Mode of ventilation
- b) FiO₂ and PEEP
- c) Tidal volume, Respiratory rate (set rate and total rate), Minute ventilation, Inspiratory flow rate
- d) Peak pressure, Plateau pressure, Compliance, and Mean airway pressure. If on a pressure-cycling mode, peak pressure during inspiration will be assumed to be the plateau pressure.
- e) Pressure during inspiration if on a pressure targeted mode (PSV, PCV, etc)

Vital Signs: Heart rate (beats/min), systemic systolic, diastolic, mean arterial blood pressure (mm Hg), and body temperature (°C), will be recorded in the eCRF.

Vital Status: Vital status will be assessed at Days 28, 60, 3 months, and 6 months. Subjects who have been discharged from the hospital will be contacted by phone. Additional information will be collected on discharge status, ventilator status, and vasopressor status at Days 28 and 60.

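### Oxygen dilution by the CO injector is not counted in the stated 0.1 FiO2 margin, nor in the FiO2 paired with blood gases drawn during dosing

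*Combined protocol and SAP*

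**What the plan says.** **Gas path.** In section 6.1.1, "the injector module will be connected between the inspiration port of the ventilator and inlet port of the humidifier". Section 2.2.7 describes a device that "matches the patient's inspiratory flow with the injected 5000 ppm CO to deliver the operator set CO concentration". Under section 6.2.2 the cylinder "contains 360 liters of 5000 ppm (0.5%) CO in room air (21% oxygen"; section 6.1.2 gives the same contents. The personalised dose is 200 to 500 ppm (section 6.1.3).

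**Oxygen monitoring.** Section 6.1.1 adds: "The gas sampling line will be placed between the outlet port of the humidifier and the patient wye as shown". Sections 2.2.7 and 6.1.4 say that the device measures inspired oxygen there and alarms on high or low values. The device is concealed from the coordinator and the ICU team.

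**Margin.** Section 5.2 justifies the severe-hypoxemia criterion for both enrolment and daily treatment. It says that the criteria "explicitly specify a safety margin of 0.1 for" FiO2. It does not say whether FiO2 means the set or the delivered value.

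**Which FiO2 is used.** In section 8.1, FiO2 is listed among the ventilator parameters, which are recorded before dosing starts. The oxygenation index uses FiO2 "and mean airway pressure obtained from the ventilator parameters". For SOFA, "The SOFA score will be calculated based on the worst values recorded in the past 24 hours", including the worst PaO2/FiO2 of the date, with no FiO2 source named. Table 5 records FiO2 with the pre-treatment and 90-minute gases, again without a source.

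**Placebo.** Section 6.2.2 says that placebo air goes through the same device in the same way. It gives no injector setting.

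**The concern.** Cylinder gas that enters after the ventilator lowers the oxygen fraction reaching the patient, and by more at higher CO doses. The supplied text does not mention this. Two things follow.

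First, section 5.2 offers its margin as protection during treatment, which is exactly when the dilution is present. The stated reserve is therefore larger than the real one for patients near the FiO2 limit.

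Second, a blood gas drawn while CO is flowing reflects the delivered oxygen. Dividing its PaO2 by the ventilator setting gives a ratio that is too low. SOFA takes the worst value of the day and does not exclude gases drawn during dosing, so a reading that is falsely low is the one more likely to be selected.

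**Working it through.** **The plan's own figures.** Section 5.2: 90 / 0.9 = 100 and 1.0 − 0.9 = 0.1. Both reproduce.

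**Inputs.** Source gas 5000 ppm CO in 21% oxygen (6.1.2, 6.2.2); injection after the ventilator (6.1.1); dose D of 200 to 500 ppm (6.1.3).

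**Formulas**, assuming ideal mixing:
- Injected share: f = D / 5000.
- Delivered FiO2 = set FiO2 × (1 − f) + 0.21 × f.
- Set value needed to deliver 0.90 = (0.90 − 0.21 × f) / (1 − f).
- Share of margin used = (set value needed − 0.90) / 0.1.

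| D (ppm) | f | Delivered at set 0.6 | Delivered at set 0.9 | Delivered at set 1.0 | Set value to deliver 0.90 | Share of margin |
|---|---|---|---|---|---|---|
| 200 | 4% | 0.584 | 0.872 | 0.968 | 0.929 | 29% |
| 300 | 6% | 0.577 | 0.859 | 0.953 | 0.944 | 44% |
| 400 | 8% | 0.569 | 0.845 | 0.937 | 0.960 | 60% |
| 500 | 10% | 0.561 | 0.831 | 0.921 | 0.977 | 77% |

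Example at 500 ppm and set 0.9: 0.9 × 0.9 + 0.21 × 0.1 = 0.831. To deliver 0.90: (0.90 − 0.021) / 0.9 = 0.977.

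The upper rows are not a corner case. Table 4 predicts 7.0% COHb, the computed target, after 90 minutes at 400 ppm for mean ARDS values.

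**Sensitivity.** If the injector meters cylinder gas as a ratio of ventilator flow, f = r / (1 + r) with r = D / 5000. The shares of margin become 28%, 55% and 69% at 200, 400 and 500 ppm. The ±10% blend tolerance in section 6.2.2 moves delivered FiO2 at set 0.9 and 500 ppm to between 0.823 and 0.837.

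**PaO2/FiO2.** If set FiO2 is the divisor, the ratio read equals the actual ratio × (delivered / set). Over set FiO2 0.4 to 1.0, it reads 1.9% to 3.2% low at 200 ppm and about 5% to 7.9% low at 500 ppm. Two cases at 500 ppm:
- PaO2 90, set 0.6: reads 150; actual 90 / 0.561 = 160.4; shift 10.4 mm Hg.
- PaO2 90, set 0.9: reads 100; actual 90 / 0.831 = 108.3; shift 8.3 mm Hg.

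Against the SD of 66 in Table 7 these are 10.4 / 66 = 0.16 SD and 8.3 / 66 = 0.13 SD.

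**Which values are exposed.** Ventilator parameters are recorded before dosing (8.1), and the reference measurements fall between 03:00 and 10:00 (8.5.1). Pre-dose LIS, PaO2/FiO2 and OI are therefore unaffected. The exposed values are the 90-minute one, any post-treatment one (Schedule of Activities, footnote B) taken while gas still flows, and a SOFA day whose worst ratio comes from such a gas.

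**Between arms.** At set 0.6 with iCO at 500 ppm, the iCO reading is 6.5% low (0.561 / 0.6). If placebo is injected at the same share, the difference between arms is nil. If placebo were at the 200 ppm share (2.6% low), it is 3.9 percentage points. If no placebo gas were injected, it is the full 6.5%. A placebo share above the iCO share would reverse the sign.

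**The case against.** The strongest reply is that the effect on the data is small and mostly outside the endpoints. Pre-dose measurements carry no dilution, the shift is about 8 to 10 mm Hg at the dose cap, and these are secondary endpoints in a trial whose primaries are safety and COHb accuracy. All of that stands. It is also true that inspired oxygen is sensed downstream with alarms, SpO2 is monitored continuously and a physician is at the bedside. These reduce the hazard, but nothing says that the oxygen reading is recorded or used.

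Four stronger readings are tempting, and the documents do not support them:
- *That all oxygenation endpoints use the ventilator FiO2.* This is explicit only for OI. It is implied elsewhere, because section 8.1 defines no other FiO2, but SOFA and Table 5 name no source.
- *That the margin is largely used up at every dose.* It is 29% at 200 ppm and passes half only at the upper doses.
- *That the error makes iCO look worse than placebo.* Placebo air dilutes too, and neither the size nor the sign of a difference can be fixed without its setting.
- *That ratios cross a scoring cut-off at 100.* The SOFA scoring in Appendix B5 was not supplied, and in section 5.2 the 100 only explains the rule.

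A last objection is that recording delivered oxygen could unblind coordinators. That is fair, and it determines where the value must be stored.

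**Conclusion.** The concern holds in limited form. By the protocol's own figures, FiO2 delivered during dosing is below the set value: by 0.028 at 200 ppm and 0.069 at 500 ppm when 0.9 is set. The 0.1 margin in section 5.2 omits this, and offsetting it takes 29% to 77% of that margin. Ratios that pair ventilator FiO2 with gases drawn during dosing read about 2% to 8% low. This is confined to values taken while gas flows and to any SOFA worst-of-day value drawn from them. Bias between arms is possible but undetermined.

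The result rests on ideal mixing, a nominal 5000 ppm source and the supplied text. Appendix A (the device manual) was not supplied and may settle the placebo setting. The point is worth correcting because the remedy is nearly free. It does not undermine the primary endpoints.

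**What to change.** - **Table 5 and section 8.5.3:** record the inspired oxygen read by the COventDS monitor with each blood gas drawn during dosing. Unblinded staff should enter it in the existing limited-access project, so that coordinators do not see it.
- **Section 8.1:** name the FiO2 source for each calculation and time point. Use the measured inspired value for PaO2/FiO2 from gases drawn during dosing, or exclude those gases from the SOFA worst-of-day ratio.
- **Section 6.1.3 or 6.2.2:** state the placebo injection setting, chosen so that dilution is comparable between arms.
- **Section 5.2:** reconcile the 0.1 margin with the dilution implied by sections 6.1.1, 6.1.2 and 6.2.2, and say whether FiO2 there means set or delivered. No clinical threshold is proposed here.

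The cost is one extra restricted data field, protocol wording and a slightly less favourable stated margin. The device already makes the measurement.
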